4.2. Protocol Violations

Major protocol violations are defined as violations liable to prevent or change the interpretation of the results of the study or may impact patient safety, affect the integrity of study data and/or affect patient's willingness to participate in the study.

The list of protocol violations will be drafted by ICTA PM and sent to sponsor for approval. The list will contain possible protocol violations (according to inclusion/exclusion criteria, disallowed treatments, minimum treatment exposure, and calendar of visits...), and significant violations which require immediate information to the Sponsor will be identified. This list may be updated in the course of the Data Management process, and will be finalized during the data review meeting before database lock.

During the data review, the impact of each violation (Minor/major) on the primary endpoint will be discussed and thus, the list of patients to be excluded from the population sets will be defined.

Patients who met protocol violation as detailed in the previous list will be listed and the number of such patient will be summarized.

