6.1 Type of trial

This is a multicenter, open label, randomized, controlled phase IIb trial.

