8.3 Registration procedure in IWRS (interactive web response system)

Registration takes place once the patient give his/her consent to participate in the study. Investigator must declare patient inclusion by entering patient data selection in IWRS (see details in Appendix 2) and, after checking all inclusion/exclusion criteria, ask for randomization.

After confirmation of randomization, the system will display the treatment arm allocated and the investigator will receive an e-mail.

A: Low-dose cytarabine

B: Low- dose cytarabine + GRASPA

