4. SUBJECT POPULATIONS

4.1. Population Definitions

The **intent-to-treat (ITT) population** will comprise all randomized patients in the groups to which they were randomly assigned, regardless of their adherence with the entry criteria, regardless of the treatment they actually received, and regardless of subsequent withdrawal from treatment or deviation from protocol.

The **per-protocol (PP) population** will comprise all patients from the ITT population without any major protocol deviation that have received trial product and have completed at least one course of treatment.

All data analysed on the ITT or PP populations will be summarized using randomized treatment.

The **safety population** will comprise all patients that have received at least one administration of trial products.

All data analysed on the safety population will be summarized using actual treatment received.

The responsibility for defining the study populations and excluding patients from the analysis will be a joint decision by the sponsor, trial statistician, investigator and trial monitor. The patients to be excluded and the reasons for their exclusion must be documented and signed by those responsible prior to database release. The documentation must be stored together with the remaining trial documentation.

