5.6.2. Secondary Endpoint Definitions and Analyses

Secondary endpoints will be assessed on both the ITT and PP populations.

5.6.2.1. Complete Remission (CR), Complete Remission with Incomplete Recovery (neutrophil or platelet recovery, CRi, CRp), Partial Remission (PR)

Definitions for CR, CRi, and PR can be found in Table 4 below. This information will be collected in the section “AML-disease evaluation.” Responses are entered by the site in accordance with various criteria. Exploratory analyses may include imputed responses (not site defined) based on the data available per the criteria in Table 4 for the derivation of response.

Table 4: Definitions of CR, CRi, PR, Relapse

Category	Definition according to protocol V4 to V6	Definition according to protocol V7
Morphologic leukemia-free state	Bone marrow blasts < 5% No extramedullary disease	
Complete remission (CR)	Morphologic CR Bone marrow blasts < 5%; absence of blasts with Auer rods; absence of extramedullary disease; absolute neutrophil count $> 1.0 \times 10^9/L$ (1000/ μ L); platelet count $> 100 \times 10^9/L$ (100 000/ μ L); patient independent of transfusions Cytogenetic CR Cytogenetic normal (in those with previously abnormal cytogenetics) Molecular CR Molecular studies negative	
CR with incomplete recovery (CRi)	All CR criteria except for residual neutropenia ($< 1.0 \times 10^9/L$ [1000/ μ L]) OR thrombocytopenia ($< 100 \times 10^9/L$ [100 000/ μ L]). patient independent of transfusions	
Partial remission (PR)	All hematologic criteria of CR; decrease of bone marrow blast percentage to 5% to 25% And normalization of blood counts	
Relapse following CR	Bone marrow blasts $\geq 5%$; OR reappearance of blasts in the blood OR Development of extramedullary disease	

Percentages of patients with CR, CR or Cri, and PR will be calculated and presented by treatment group. All other subjects will be considered non-responders for determining the denominator. This objective response rate data (i.e. CR, CRi or PR) will be analyzed based on a logistic regression model with both treatment and PS included in the model. The treatment effect will be summarized with an adjusted Odds Ratio (OR) and 95% confidence interval. Percentage of patients with objective response will be calculated and associated exact 95% CIs will be presented by treatment group.

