5.6.2.2. Progression-Free Survival (PFS)

PFS was originally defined as death due to progression in the protocol. However, to be consistent with regulatory guidance, which considers death from any cause in its definition, this endpoint was modified to be time elapsed between randomization and disease progression or death from any cause. Patients not known to have any of these events will be censored on the date they were last known to be event-free.

Progressive disease (PD) will be defined according to the section “AML-DISEASE EVALUATION” in the e-CRF as any of the following

- At least a 25% increase of BMBC compared with baseline (defined in the section “AML history / BM evaluation at baseline”, Bone Marrow Aspirate - Analyte - Blast)
- At least a 50% increase of PBBC compared with baseline
- Presence of extramedullary disease

Potential PD events presented by the patients will be reviewed and approved before database lock.

The methods for the analysis of PFS will be the same as those for OS. Specifically, PFS will be analyzed at the time of final analysis using a stratified log-rank test (stratified by PS) and displayed using Kaplan-Meier curves. Furthermore, a Cox model will also be used to test the effect of treatment and will include terms for prognostic factors (PS, age and karyotypic group).

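### In an open-label trial, per-protocol exclusions and, separately, approval of progression events are decided before lock with no provision for masking and with the grading and approval rules left open

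*SAP*

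**What the plan says.** - **Masking.** Protocol 6.1: "This is a multicenter, open label, randomized, controlled phase IIb trial". Protocol 8.3 adds that after randomization "the system will display the treatment arm allocated and the investigator will receive an e-mail".
- **Who excludes patients.** Under SAP 4.1, and protocol 15.1 in nearly the same terms, the choice "will be a joint decision by the sponsor, trial statistician, investigator and trial monitor". The stated safeguard is: "The patients to be excluded and the reasons for their exclusion must be documented and signed by those responsible prior to database release".
- **On what basis.** SAP 4.1 fixes two exposure conditions for the per-protocol (PP) set: study product was given, and one course or more was finished. For the rest, SAP 4.2 defines a major violation broadly, by whether it could alter how the results are read or could touch safety, data integrity or willingness to take part. It names categories of violation. The list is drafted at the CRO, approved by the sponsor, may change during data management, and "will be finalized during the data review meeting before database lock". At that review, "the impact of each violation (Minor/major) on the primary endpoint will be discussed and thus, the list of patients to be excluded" from the analysis sets is defined.
- **Progression.** SAP 5.6.2.2, on PFS: "Potential PD events presented by the patients will be reviewed and approved before database lock". No approver and no approval rule is named. On response data, SAP 5.6.2 says: "Responses are entered by the site in accordance with various criteria".

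Neither document says whether treatment codes or outcomes are withheld at the violation review or at the approval of progression.

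**The concern.** Deciding before lock and signing before release are sound protections when the people deciding do not know the arm. Here at least one named decision maker does, and sites also know who has died. A violation judged patient by patient for its bearing on OS can be graded with arm and outcome in mind, and so can a borderline progression event. Signing records such a choice but does not prevent it.

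The PP analysis is one of the stated sensitivity checks on OS (protocol 15.3.1, SAP 5.6.1). The SAP Introduction says that conclusions will weigh effect sizes across several endpoints and not rest on the primary analysis alone. Results exposed to such choices would therefore feed into the decision on a phase 3 trial.

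**Working it through.** The plan gives no figure on this point, so the check sets the passages side by side and then gauges how much room they leave.

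**1. Who can know the arm.** The investigator is told it (protocol 8.3). The sponsor makes each GRASPA bag for one named patient from a prescription (protocol 9.6). The monitor checks drug accountability and source documents (protocol 13). So up to three of the four parties in SAP 4.1 can know the arm of some or all patients. The documents do not say what the trial statistician sees.

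**2. A control used elsewhere.** Protocol 11.6 keeps survival curves from the IDMC and keeps sponsor staff out of meetings that look at data by arm. No matching control is described for the data review.

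**3. Room for judgement on progression.** SAP 3.5.1 and protocol 4.3.2 count resistant disease, relapse or death as PFS events. Protocol Table 3 measures resistant disease from the nadir, repeated at least 7 days apart. SAP 5.6.2.2 counts a 25% rise in marrow blasts or a 50% rise in peripheral blasts from baseline, or extramedullary disease. A patient whose blasts fall and then climb part of the way back can meet the nadir rule and not the baseline rule. The approval step does not say which rule decides.

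**4. Which results can move.**

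| Result | Exposed? | Reason |
|---|---|---|
| OS, ITT | No | All randomized patients, death from any cause (SAP 4.1, 5.6) |
| OS, PP | Yes | Membership depends on the review |
| PFS, ITT and PP | Yes | Event dates depend on approval |
| Transfusions, hospitalizations | Yes | Counts stop at progression (SAP 5.6.2.4, 5.6.2.6) |

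**5. Illustration of scale.** The assumptions are exponential survival, 41 control and 82 GRASPA patients, and no true effect. All choices run in one direction, so this is a worst case and not a forecast.

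*OS.* Median 6.4 months in both arms (the control figure in the SAP Introduction), cutoff at 24 months, and the k earliest GRASPA-arm deaths removed. The hazard ratio (HR) comes from a Cox model (600 runs per row) and from the rate ratio (deaths/time in GRASPA) ÷ (deaths/time in control) (4,000 runs per row).

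| k | Cox median HR | Cox P(HR ≤ 0.80) | Rate-ratio median HR | Rate-ratio P(HR ≤ 0.80) |
|---|---|---|---|---|
| 0 | 1.006 | 0.103 | 1.003 | 0.131 |
| 4 | 0.933 | 0.257 | 0.944 | 0.197 |
| 8 | 0.900 | 0.308 | 0.901 | 0.285 |

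One caution applies. If finishing a course means surviving 28 days (28/30.4 = 0.92 month), the chance of dying sooner is 1 − exp(−0.693 × 0.92/6.4) = 0.095. That is about 0.095 × 82 = 7.8 GRASPA and 0.095 × 41 = 3.9 control patients. The exposure condition would drop these in both arms. The table shows what removal from one arm only would do.

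*PFS.* Median 2 months in both arms (the control figure in SAP 5.1), and k GRASPA-arm events dated 28 days later (600 runs per row).

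| k of 82 | Share of arm | Median HR |
|---|---|---|
| 0 | 0% | 0.990 |
| 8 | 9.8% | 0.972 |
| 16 | 19.5% | 0.933 |
| 24 | 29.3% | 0.898 |

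**The case against.** The other side has a good deal to say.

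- The documents are silent on masking; they do not state that the reviews are unmasked. SAP 4.2 can be read as ordinary grading, which asks whether a type of violation could bias OS without looking up anyone's survival. The violation list is a separate document and may already hold fixed grades.
- Exclusions can be audited. The SAP plans a table of reasons for PP exclusion (14.1.2.2) and listings of analysis sets and deviations.
- The rule for calling GRASPA promising uses the OS hazard ratio (protocol 15.3.1, SAP 5.1), and the OS analysis is on the ITT population. PP is not the only sensitivity analysis: SAP 5.6.1 also splits by amendment and fits an adjusted Cox model.
- Listing 16.2.6.2 mentions central readings.
- Masked listings cannot blind an investigator who treated the patient.

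Most of this stands and limits the reach of the point. It does not remove it. A listing title is not a described process. A later audit shows which choices were made, not whether arm or outcome guided them. An approval step with two progression definitions and no rule is open on its face.

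A reader might infer more than the text supports:

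- **That the primary result is compromised.** It is not. ITT membership and death from any cause do not pass through either step.
- **That progression is approved after the discussion of impact on OS.** That discussion concerns violations only; progression approval is a separate sentence in another section.
- **That one control patient, 1/41 = 2.4% of the arm, or five, 5/41 = 12.2%, measures the bias.** These are shares of an arm, not changes in an estimate. A progression event that is not approved leaves the patient in the analysis, and a later progression or death still counts, so only the event time shifts.

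**Conclusion.** The point holds as a gap that should be closed, of moderate weight. As written, the plan allows PP membership and progression dates to be settled with knowledge of arm or outcome. That such knowledge would be used is an inference from the open design, the listed decision makers and the absence of any masking provision; no passage states it.

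On size, no planned figure changes. Under the one-directional assumptions above, a handful of selective exclusions could pull a null PP hazard ratio for OS to about 0.90-0.93 and raise the chance of a value at or below 0.80 from roughly 0.10-0.13 to 0.20-0.31. PFS is harder to move: delaying 8 events shifts the hazard ratio by about 0.02, and reaching 0.90 takes 24 of 82.

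**What to change.** 1. In the SAP, fix the list of major deviations and grade them by type of violation, not by an individual patient's outcome, before the data review meeting.
2. Apply the two PP exposure conditions by program. They need dosing data, which would reveal the arm if shown to reviewers. State what counts as a finished course.
3. Have the sponsor, statistician and monitor classify the remaining violations from listings without arm, GRASPA dosing, survival or progression status. Limit the investigator to answering factual queries.
4. Reconcile the progression definition in SAP 5.6.2.2 with protocol Table 3 and SAP 3.5.1. Derive progression by program from recorded blast counts and extramedullary findings, and log every change made at review. Report PFS on programmed progression and on site-reported or approved progression, one as a sensitivity analysis for the other.

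The cost is the preparation of masked listings for a meeting already planned and one extra PFS analysis. No patients, visits or reviewers are added. Masking stays imperfect for anyone who already knows a patient's arm, including a monitor who has checked that site's drug accountability. Grading by type and programmed derivation therefore do most of the work.

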5. STATISTICAL METHODS

5.1. Sample Size Justification

The sample size calculation is based on the original primary efficacy endpoint (PFS). We assumed 75% improvement in median PFS in the GRASPA plus LDAC group (treatment) compared to median PFS in the LDAC group (control). This corresponded to a median PFS of 2 months for the null hypothesis and a median of 3.5 months for the alternative hypothesis. An assumption of 24 months of accrual time and whole study duration of 48 months was used. No dropout rate was taken into consideration.

With a two-sided 5% level significance test and a power of 80%, taking into account the unbalanced group size (1 : 2), a total of 117 patients should be enrolled in order to observe 117 PFS events.

The study was designed based on the initial primary endpoint using group sequential methodology, allowing for interim analysis for futility. In order to account for this, the sample size was increased from 117 to 123 patients (41 in the LDAC group and 82 in the GRASPA plus LDAC group).

However, the sponsor amended the study, and the primary endpoint was changed from PFS to OS. It is acknowledged that the study is not powered to detect a statistically significant difference in OS; rather this is a proof of concept signal seeking study. In light of this, the one-sided significance level will be 0.025.

A decision as to whether GRASPA appears to be a promising drug in this indication will be based on the numerical values for the hazard ratio for OS. A hazard ratio of ≤ 0.80 will indicate a 20% numerical reduction in the death rate on average over time in the GRASPA group compared to control.

5.2. General Statistical Methods and Data Handling

5.2.1. General Methods

All outputs will be incorporated into Microsoft Excel or Word files, sorted and labeled according to the International Conference on Harmonisation (ICH) recommendations, and formatted to the appropriate page size(s).

Tabulations will be produced for appropriate demographic, baseline, efficacy, pharmacokinetic and safety parameters. For categorical variables, summary tabulations of the number and percentage within each category (with a category for missing data) of the parameter will be presented. For continuous variables, the mean, median, standard deviation, minimum and maximum values will be presented. Time to event data will be summarized using Kaplan-Meier methodology with median time to event and associated 2-sided 95% confidence intervals, as well as percent of censored observations.

Formal statistical hypothesis testing to be performed on the primary efficacy endpoint will be conducted at the 1-sided, 0.025 level of significance. Secondary efficacy endpoints will be conducted at the 2-sided, 0.05 level of significance. Summary statistics will be presented, as well as confidence intervals on selected parameters, as described in the sections below.

Any patient not known to have had an event (death/progression) at the time of analysis will be censored based on the last recorded date on which the patient was known to be event-free.

For numeric secondary endpoints (e.g. quality of life scores) the analysis of these endpoints will be based on observed data. For repeated measures analyses using mixed models, all available data will be included in the analysis, and missing data will not be imputed.

5.2.2. Computing Environment

All statistical analyses will be performed using Statistical Analysis Systems (SAS®) release 9.2 or higher, unless indicated otherwise. All computer programs will be developed and validated according to ICTA PM (CRO) standard operating procedures.

Medical History and adverse events will be coding using MedDRA version 15.1 or higher. The intensity of AEs will be graded according to the NCI-CTCAE (version 4.0). Concomitant medications will be coded using World Health Organization (WHO) Drug Dictionary, version March 2013.

5.2.3. Methods of Pooling Data

Not applicable to the present study.

5.2.4. Adjustments for Covariates

No formal statistical analysis that adjusts for possible covariate effects is planned.

5.2.5. Multiple Comparisons/Multiplicity

Multiplicity is not of concern for this study with a single primary efficacy endpoint.

5.2.6. Subpopulations

Analyses (estimated treatment effects and 95% confidence intervals) will be undertaken in relation to OS, PFS and objective response according to the following subgroups and presented in Forest Plots:

- Gender (male/female)
- ECOG PS (0 versus 1 versus 2)
- Age (< 70 / ≥ 70)
- Karyotype (Intermediate risk / High risk)
- Baseline bone marrow blasts, % (< 20% / ≥ 20% to ≤ 30% / > 30%)
- LDH levels at baseline (normal/elevated/unknown)

- FAB (French-American-British) Classification of AML (M1/2 vs. M4/5 vs. M0/6/7)

Other subgroups may be investigated in exploratory analyses.

5.2.7. Withdrawals, Dropouts, Loss to Follow-up

Subjects who withdrew from the study were not to be replaced.

5.2.8. Missing, Unused, and Spurious Data

In general, there will be no substitutions made to accommodate missing data points. All data recorded on the CRF will be included in data listings that will accompany the clinical study report.

5.2.9. Visit Windows

Assessments are taken at specific study days in relation to the first day of LDAC (Study Day 1). LDAC is administered each day following and including Day 1, for 10 consecutive days (D1-D10). Patients in the treatment group are also administered GRASPA at Day 11. This will occur each course, which is 28 days +/- 3 days.

Biological assessments will be performed (if applicable) at D1, D5, D9, D13, D18, D23 and D27 during each course (+/- 2 days). The quality of life questionnaire and information about both hospitalizations and transfusion needs will be completed at each visit.

Follow-up visits will occur at the end of study treatment every 3 months +/- 2 weeks (i.e. M3, M6, M12,...). At minimum, a phone call will be performed every 4 months +/- 1 week after end of treatment for safety assessments.

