8.4 Study treatment administration

All patients enrolled, randomized in Arm A or B, will receive successive 28-day courses of subcutaneous low-dose cytarabine 40 mg daily (or 20 mg twice daily) for 10 days per course (from day 1-D1 to day 10-D10), each course occurring every 28 days +/- 3 days, for a duration up to 24 months. SPC for Cytarabine Hospira and Pfizer are attached in Appendix 1 as example. Please refer to country-specific approved Cytarabine SPC for country-specific information.

Following the implementation of Amendment 4, patients randomized in arm B treatment will receive subcutaneous low-dose cytarabine, as described above, and GRASPA 100 IU/kg, given as an intravenous infusion at **Day 11** of each 28-day course.

Required documents such as **Investigator's prescription of GRASPA and Patient's pretransfusional status** (refer to section 9.6) should be sent at ERYTECH Pharma 2 days before the schedule day of GRASPA administration, i.e. Day 9.

In the event the patient cannot receive GRASPA treatment at the planned date (i.e. manufacturing failure) or if GRASPA treatment received on site is not suitable for administration (e.g. transport or cold chain impairment, rupture of bag...), investigator and ERYTECH Pharma will discuss the best treatment approach for the patient:

- Restart manufacture for a new bag of GRASPA (delay GRASPA administration with max one week), if acceptable for the patient.
- Switch the patient to appropriate alternative treatment, at investigator's decision.
 - If the switch occurred before the first GRASPA administration, then the patient will be replaced, as defined in section 7.6.
 - If the switch occurred after at least one administration of GRASPA, treatment for next blocks afterwards will be at investigator's decision (GRASPA will not be resumed if delayed more than 2 weeks; refer to section 8.5.4 "Dosage modifications of GRASPA" and 8.11 "end of study treatment").

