8.5.4 Dosage modifications for GRASPA

- If patient cannot receive GRASPA, for another reason than an adverse event, treatment may be postponed no later than one week after the initial scheduled day. A minimum two weeks interval between GRASPA infusions must be insured.
- In case of allergic reaction during administration, stop the administration immediately and then to administer the necessary symptomatic treatments, according to standard of care. Further administration of GRASPA will be at investigator judgment, considering possibility of premedication anticipated for such case.
- In case of any Grade 3 or 4 adverse event related to GRASPA occurring in two successive infusions, GRASPA should be discontinued.
- In the event of bilirubin levels >3 times upper limit of normal or transaminase levels >10 times upper limit of normal, treatment with GRASPA should be discontinued.

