8.7 Laboratory assessments

8.7.1 Biological parameters

Biological assessment will be performed according to the investigational center procedure at inclusion, and then, at D1, D5, D9, D13, D18, D23 and D27 of each course of chemotherapy (± 2 days).

Following measurement should be performed:

- Hematology: Complete Blood Count (CBC), platelets;
- Coagulation parameters: Prothrombin Time (PT), activated Partial Thromboplastin Time (aPTT), fibrinogen, antithrombin III, INR;
- Chemistry: bicarbonate, sodium, potassium, calcium, creatinine, creatinine clearance (calculated by Cockroft & Gault formula), albumin, bilirubin, alanine amino transferase (ALT), aspartate amino transferase (AST), alkaline phosphatase, gamma glutamyl transpeptidase (GGT), lactate dehydrogenase, glucose, cholesterol, triglyceride, lipase, amylase;
- Serologic test for HIV, B and C hepatitis will be made at inclusion only, if needed.
- Serum pregnancy test for women with childbearing potential at inclusion and end of treatment.

Assessed and signed anonymized lab reports must be sent to sponsor/representatives as soon as possible after receiving the results for protocol required tests as well as for any testing performed for management of AEs.

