5.8.2. Laboratory Data

5.8.2.1. Haematology, Coagulation, Biochemistry tests

Biological parameters will be described at inclusion, D1, D5, D9, D13, D18 and D23 of each course of chemotherapy. The concerned biological parameters are the followings:

- Haematology
 - Haemoglobin (g/dL)
 - Hematocrit (%)
 - Erythrocytes (T/L)
 - Leukocytes (G/L)
 - Neutrophils (G/L)
 - Blasts (%)
 - Platelets (G/L)
- Blood coagulation
 - Activated Partial Thromboplastin Time (aPTT) (sec)
 - Prothrombin time (%)
 - Fibrinogen (g/L)
 - Antithrombin III (%)
 - INR
- Blood biochemistry
 - Albumin (g/L)
 - Plasma Bicarbonate (mmol/L)
 - Creatinine clearance (mL/min)
 - Serum Creatinine
 - Glycaemia (mmol/L)
 - Alkaline Phosphatase (U/L)
 - AST (U/L)
 - ALT (U/L)
 - Cholesterol (mmol/L)
 - LDH (U/L)
 - Gamma-GT (U/L)
 - Bilirubin (μmol/L)
 - Triglycerides (g/L)
 - Sodium (mmol/L)
 - Potassium (mmol/L)
 - Calcium (mmol/L)
- Pancreas
 - Lipase (U/L)
 - Amylase (U/L)

Raw results as well as absolute and relative change from baseline will be described at each timepoint between treatment groups.

Absolute change in the biological parameter between visit V_i and baseline will be calculated according to the formula: $\text{biological parameter at } V_i - \text{biological parameter at baseline}$

Relative change in biological parameter between visit V_i and baseline will be calculated according to the formula: $\frac{\text{biological parameter at } V_i - \text{biological parameter at baseline}}{\text{biological parameter at baseline}} \times 100$

All laboratory data will be provided in data listings. A subset listing will be presented for all clinically significant abnormal laboratory values. Data will be summarized by treatment group and patients with laboratory values of NCI-CTCAE grade 3 or 4 will be identified.

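### SAP 5.8.2.1 leaves D27 out of the safety-lab summary over time, and its arm B D13 and D18 rows can include pre-infusion values when GRASPA is delayed

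*SAP*

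**What the plan says.** **Schedule.** Protocol 8.7.1 requires safety labs "at D1, D5, D9, D13, D18, D23 and D27 of each course of chemotherapy", with a two-day tolerance. Protocol 8.10 and Table 4 give the same seven days, and SAP 5.2.9 repeats them: "Biological assessments will be performed (if applicable) at D1, D5, D9, D13, D18, D23 and D27 during each course (+/- 2 days".

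**Clock.** SAP 5.2.9 counts from cytarabine, not from the infusion: "Assessments are taken at specific study days in relation to the first day of LDAC (Study Day 1". For arm B it adds: "Patients in the treatment group are also administered GRASPA at Day 11".

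**Permitted delay.** Under protocol 8.5.4, when the reason is not an adverse event, "treatment may be postponed no later than one week after the initial scheduled day". Protocol 8.4 allows the same margin when a bag has to be remade: "delay GRASPA administration with max one week".

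**Summary.** SAP 5.8.2.1 lists the days to be tabulated: "Biological parameters will be described at inclusion, D1, D5, D9, D13, D18 and D23 of each course of chemotherapy". It continues: "Raw results as well as absolute and relative change from baseline will be described at each timepoint between treatment groups". D27 is not in the list, and nothing ties a value to the infusion actually given in that course. Protocol 15.3.3 plans laboratory summaries over time and excludes no scheduled day.

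**The concern.** Two features of the lab summary do not fit the way the drug is given.

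First, a sample that both documents schedule in every course has no row in the table meant to show laboratory values over time. SAP 5.8.2.2 does describe amino acids and asparaginase at D27 for patients included after the amendment. Drug activity is therefore summarised on a day whose safety labs are not.

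Second, D13 and D18 are the first two scheduled lab days after an on-time infusion. A reader will take those arm B rows as showing the early effect of GRASPA on fibrinogen, antithrombin III, lipase, amylase, transaminases, bilirubin and glucose. If the infusion was late, some of those values were drawn before it. Arm A has no infusion, so the mixing occurs in one arm only. If GRASPA does move these parameters, it pulls the D13 and D18 rows toward showing less effect.

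**Working it through.** The plan states no figure to reproduce here. The check is day arithmetic.

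**Inputs**
- Lab days D1, D5, D9, D13, D18, D23 and D27, each ±2 days (protocol 8.7.1, SAP 5.2.9).
- Scheduled infusion D11 (protocol 8.4 and 9.2, SAP 5.2.9).
- Delay d from 0 to 7 days (protocol 8.4, 8.5.4).
- The D1 draw of a later course is taken at most 3 days before that course starts (protocol Table 4, note f).

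**Step 1: what leaving out D27 removes.** It is 1 of 7 scheduled samples per course. After an on-time infusion, D23 is 23 − 11 = 12 days later and D27 is 27 − 11 = 16 days later. With a 7-day delay they are 23 − 18 = 5 and 27 − 18 = 9 days later.

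**Step 2: how far the next D1 draw covers the gap.** In a 28-day course the next D1 falls on day 29, so its draw is on day 29 − 3 = 26 to day 29. The D27 tolerance runs from day 25 to day 29. The two largely coincide for a patient who starts another course. In a final course no next D1 exists. Protocol Table 6 and the end-of-treatment and follow-up lists in 8.10 contain no haematology, coagulation or chemistry panel. D27 is then the last scheduled safety lab.

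**Step 3: effect of a delay.** The infusion falls on day 11 + d. Nominal D13 is 2 − d days after it and nominal D18 is 7 − d days after it. The tolerance ranges are D11–D15 and D16–D20.

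| Delay d | Infusion | Nominal D13 | Days of D11–D15 before infusion | Nominal D18 | Days of D16–D20 before infusion |
|---|---|---|---|---|---|
| 0 | D11 | 2 after | 0 | 7 after | 0 |
| 1 | D12 | 1 after | 1 | 6 after | 0 |
| 2 | D13 | same day | 2 | 5 after | 0 |
| 3 | D14 | 1 before | 3 | 4 after | 0 |
| 4 | D15 | 2 before | 4 | 3 after | 0 |
| 5 | D16 | 3 before | 5 | 2 after | 0 |
| 6 | D17 | 4 before | 5 | 1 after | 1 |
| 7 | D18 | 5 before | 5 | same day | 2 |

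From d = 3 a sample on nominal D13 always precedes the infusion. From d = 5 the whole D13 range does. Part of the D18 range does at d = 6 and 7. The D23 range (D21–D25) and the D27 range (D25–D29) start after D18, the latest permitted infusion day. They are post-infusion in every permitted case, and 5.8.2.1 tabulates only one of the two.

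**Step 4: size of the mixing.** Let s be the share of arm B D13 values drawn before the infusion and Δ the mean GRASPA effect at D13. The row then shows (1 − s)Δ of that effect. The documents do not give s. Purely as assumptions, s = 0, 10% and 20% leave 1.00Δ, 0.90Δ and 0.80Δ.

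**The case against.** The strongest reply is that little safety information is lost. SAP 5.8.2.1 lists all laboratory data and identifies patients with grade 3 or 4 values without limiting the days. SAP 8.1 plans shifts to the worst post-baseline value for biochemistry, haematology and coagulation. Protocol 11.1.2.1 has abnormal labs reported as adverse events unless every exception criterion is met. No test or decision rule rests on the day-by-day table. All of this stands and keeps the point small. Those outputs do not, however, show timing or recovery, and they do not correct the D13 and D18 rows.

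Four stronger readings are tempting, and the documents do not support them.

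- *The ±2-day windows misfile pre-infusion D11 samples as D13.* The D9 and D13 ranges do share D11 (9 + 2 = 13 − 2 = 11). But the tolerance says when samples may be taken; no rule assigns results to rows by it. Table 4 schedules no safety lab on D11. The missing tie-break is a matter of detail.
- *D27 is dropped from the analysis, or is the only late lab.* It is absent only from the by-timepoint description, and for continuing patients the next D1 draw is at a similar time.
- *A known share of the toxicity is hidden.* Neither document says how often infusions are late. Nor would the whole change from baseline shrink by s, because patients have by then had up to ten days of cytarabine and their pre-infusion change need not be zero.
- *The main table should be re-anchored to the infusion.* With a 7-day delay, an arm B value 2 days after infusion lies on cytarabine day 20, compared with day 13 in arm A. Counting from cytarabine keeps the shared drug aligned, which is a good reason to leave the main display as it is.

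**Conclusion.** The point holds as a gap in the descriptive safety tables. The D27 omission follows directly from the text: both documents schedule the sample and SAP 5.8.2.1 does not tabulate it. It matters most in a patient's final course, where D27 is the last scheduled safety lab. The timing point is conditional. Arm B D13 rows include pre-infusion values when samples are taken on the nominal day and the infusion is 3 to 7 days late; D18 rows can do so after 6 or 7 days. A delay of 1 or 2 days matters only for D13 samples drawn early or on the infusion day.

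The size of the mixing cannot be stated, because the frequency of delays is not given. Any understatement also assumes that GRASPA shifts the parameter and that pre-infusion values carry none of that course's effect. A reader might infer that the trial's laboratory safety conclusions are biased as a whole. They are not shown to be: listings, grade 3/4 identification, worst-value shifts and adverse event tables do not depend on nominal day, and overall survival and the other efficacy analyses are untouched.

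**What to change.** 1. In SAP 5.8.2.1, add D27 to the days described in each course.
2. Keep the table counted from first cytarabine as the main between-arm display.
3. Add a supplementary arm B summary that classes each lab value as before or after that course's actual infusion date. Treat a sample taken on the infusion day as pre-infusion unless a clock time shows otherwise.

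Protocol 8.10 requires the date and time of study treatment. For labs it mentions only a sample date, and that under the inclusion visit; later visits refer to signed lab reports. The same-day convention is therefore needed, and the summary assumes that sample dates are held for every course. The cost is SAP wording, a small amount of programming, one more table and slightly uneven numbers per time point. No new data and no change to patient management are involved.
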